5. TRIAL OBJECTIVES AND PURPOSE

5.1 Primary objective

To evaluate the safety and tolerability of long-term intermittent use of lasmiditan 100 mg and of lasmiditan 200 mg, as the first and as a second dose, in the acute treatment of migraine.

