10. STATISTICS

Prior to locking the database, a detailed statistical analysis plan will be developed before any receipt of study data and decisions will be made regarding the integrity of subject data for inclusion in the statistical analysis. All safety analyses will be based on the Safety Population. The efficacy analyses and baseline characteristics will be based on the Intent-to-Treat (ITT) and mITT population. The Per Protocol Population will be used to support the ITT analyses.

The primary objective of this study is to evaluate the safety and tolerability of long-term intermittent use of lasmiditan 100 mg and of lasmiditan 200 mg, as the first and as a second dose, in the acute treatment of migraine.

The secondary objective of the study is to explore the long-term efficacy of lasmiditan 100 mg and lasmiditan 200 mg in terms of headache response over time.

Summary analysis of the safety and efficacy of the use of a second dose of lasmiditan for either rescue or recurrence will be performed only in the subjects that actually took a second dose of study drug within 24 hours of the first dose. Analysis will be performed on the subset of subjects that dosed for rescue and on the subset that dosed for recurrence of migraine.

Data from all investigative sites will be pooled for all planned analyses. Analysis of individual site findings will be considered if necessary. For those measures that are summarized using change from baseline scores, observed scores may also be presented descriptively.

Any changes in the data analysis methods described in the protocol will require an amendment only if it changes a principal feature of the protocol. Any other changes to the data analysis methods described in the protocol and the justification for making the change will be described in the statistical analysis plan as well as the clinical study report. Additional exploratory analyses will be conducted as deemed appropriate. All data listings, summaries and analyses will be performed by Quintiles.

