10.5.1 Adverse Events

AEs will be coded by the Medical Dictionary for Regulatory Activities (MedDRA) preferred terms, and all summary tables for AEs will be organized by these categories. Frequency counts and percentages will be presented for subjects with AEs within each system organ class and preferred term, separated by treatment arm and dose (the first dose and the second dose for recurrence or rescue or alternative rescue medication). Both subjects ever experiencing an event as well as total events will be presented. Descriptive statistics will also be calculated for each treatment arm and dose (initial and second dose for recurrence or rescue medication) for AE relationship and AE severity. If multiple intensities are reported for a given AE for a subject, the most severe intensity will be counted. A separate, similar analysis will be conducted for TEAEs.

An AE with the date of onset on or within 48 hours after a dose of study drug, or an event that worsens in intensity within 48 hours of a dose of study drug will be considered a TEAE. An AE that occurs in the interval after 48 hours of dosing until the next migraine is dosed will not be considered a TEAE.

SAEs and TEAEs that resulted in termination of the study drug and withdrawal from the study will be presented.

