### **5.4 Analysis of First and Second Doses**

Any analyses based on first dose will only include data observed up to the time of dosing with a second dose. These summaries will be presented based on the first dose taken. The exception to this is the secondary endpoints at the 2-hour time point; if a second dose is taken before the 2-hour time point, the subject will still be included in the summary at 2 hours and will be analysed as having not achieved headache pain-free or MBS-free status at 2 hours.

Any analyses based on the second dose will only include data observed on or after the time of dosing with a second dose. Analyses based on the second dose will be done for both the rescue and recurrence subpopulations.

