### **12.1 Adverse Events**

An AE with the date of onset on or within 48 hours after a dose of study drug, or an event that worsens in intensity within 48 hours of a dose of study drug will be considered a treatment-emergent adverse event (TEAE). Other AEs are defined as those occurring after randomization but not considered to be treatment-emergent.

Descriptive statistics for both number of subjects ever experiencing an event as well as for the total number of events will be presented. Furthermore, descriptive statistics will also be calculated for each treatment group irrespective of first or second dose for AE relationship and AE severity. If multiple intensities are reported for a given AE and subject, then the most severe intensity will be counted. A separate, similar analysis will be conducted for TEAEs.

AEs with a missing start date will be assumed to be treatment-emergent, except in situations described in Appendix 1. If a subject takes at least one dose of study drug, but the date and time of dosing is missing in the e-diary, all AEs for that subject will be considered treatment-emergent, if the AEs occur between available date of dosing as recorded only in CRF for up to 48 hours (2 days) post recorded date of dosing. If the date and time of the second dose is missing in e-diary then all AEs for that subject will be considered as treatment emergent due to second dose, if AEs occur between available date of dosing in CRF for second dose, and an ending boundary of 2 days after recorded date of dosing with second dose, inclusive. See Appendix 1 for derivations related to partial dates and times.

Nausea and/or vomiting reported as adverse events during a migraine by any subject that also noted these as characteristics of their migraine will be presented by treatment groups and not be considered related to treatment but rather an underlying condition of the migraine.

AEs will be coded by the Medical Dictionary for Regulatory Activities (MedDRA) version 21.0.

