Unless otherwise stated, frequencies of adverse events will be displayed by applicable treatment group and overall. AEs will be sorted alphabetically by system organ class (SOC), preferred term (PT), and frequency. For the overall summary of AEs, both total subjects ever experiencing an event as well as total number of events will be presented. For all other summaries, subjects with multiple occurrences of the same AE preferred term will be counted once within the corresponding system organ class and preferred term.

Adverse events will be summarized by treatment arm in the following tables:

- Overall summary of AEs for Safety Population, 6-month, and 12-month population including:
  - All AEs
  - TEAEs
  - Other AEs
  - Related TEAEs
  - AEs leading to study discontinuation
  - Serious AEs
  - Related serious AEs
  - Deaths

- Incidence of All AEs and Other AEs by SOC for the Safety Population and Pre-administrative hold Population.
- Incidence of TEAEs by SOC for the Safety Population, 6 month and 12 month Safety Population.
- Incidence of TEAEs by decreasing frequency of PT for the Safety Population and Pre-administrative hold Population.
- Incidence of TEAEs occurring in more than 2% of subjects by quarter for Safety Population.
- Incidence of TEAEs and SAEs by SOC, PT and Doses for the Safety Population, 6-month and 12-month Safety Population.
- Summary of TEAEs by SOC, PT, and migraine attack sequence for the Safety Population.
- Summary of TEAEs by PT and migraine attack sequence for subjects that treated 5 or more migraine attacks in the Safety Population
- Summary of TEAEs occurring in more than 2% of subjects by PT for the Safety Population.
- Incidence of all SAEs by SOC for the Safety Population, 6 month and 12 month Safety Population.
- Incidence of All AEs leading to study discontinuation for Safety Population, 6-month and 12-month Population.
- Listing of All AEs leading to study discontinuation or death.
- Incidence of serious TEAEs for Safety Population, 6-month and 12-month Population. In addition, listings of these will be presented for Pre-Administrative Hold Population.
- Listing of Serious AEs.
- Time to onset and duration of TEAEs occurring in more than 2% of subjects relative to dosing regardless of second dose. If the time of adverse event is missing, no imputation will be performed for this presentation. The most frequent TEAE list will be finalized before interim soft lock and final database lock.

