- Subgroup analysis will be presented for subject with cardiovascular risk factors. TEAE will be compared among subjects with and without CVRF for individual event for Safety population. They will be tested with chi-squared test or fisher's exact test as appropriate with respect to sample size and all comparisons will be done at level of significance of 0.05.

Above tables will be presented for various types of AE criteria as below:

1. Incidence of TEAE table will be provided by-subject analysis. For this analysis, the adverse events will be reported out of total number of subjects in each treatment group regardless of whether a second dose is taken.
2. Similar events as Point #1 will be reported when only 1 dose was taken and additionally when 2 doses were taken.

3. Incidence of serious adverse events table will be reported by-subject analysis for each treatment group regardless of whether a second dose is taken.
4. Similarly, to Point # 2, serious events will be reported when only 1 dose was taken and additionally when 2 doses were taken.
5. TEAEs summary will be provided by each treated migraine analysis. For this analysis, the adverse events will be reported out of total number of treated migraines for each treatment group regardless of second dose.
6. Additionally TEAE by-subject analysis will be provided for treated 1st migraine attack, 2nd migraine attack, 3rd migraine attack, 4th migraine attack, 5th migraine attack, 10th migraine attack, 15th migraine attack, 20th migraine attack
7. Specific most common TEAEs will be reported in descriptive statistics (n, mean, median, SD, Minimum and maximum) by proportion of treated migraines attacks in subjects experiencing the TEAE at least once. This data will be presented out of total number of subjects in each treatment group. TEAEs will be reported if 2% or more of subjects any any treatment group report the event.

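### SAP 12.1 does not carry out the rescue and recurrence split that Protocol 10 plans for second-dose safety, and it drops the dose split for relationship and severity

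*SAP*

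**What the plan says.** Protocol 5.1 sets the primary objective as the safety and tolerability of each dose level "as the first and as a second dose, in the acute treatment of migraine".

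Protocol 10 plans a summary of safety and efficacy in subjects who took a second dose within 24 hours of the first, and adds: "Analysis will be performed on the subset of subjects that dosed for rescue and on the subset that dosed for recurrence of migraine".

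Protocol 10.5.1 plans adverse event tables "separated by treatment arm and dose (the first dose and the second dose for recurrence or rescue or alternative rescue medication"). For relationship and severity it says: "Descriptive statistics will also be calculated for each treatment arm and dose (initial and second dose for recurrence or rescue medication").

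SAP 12.1 lists one table as "Incidence of TEAEs and SAEs by SOC, PT and Doses for the Safety Population" (also for the 6-month and 12-month safety populations). Its numbered point 2 reads: "Similar events as Point #1 will be reported when only 1 dose was taken and additionally when 2 doses were taken". Point 4 does the same for serious events. Relationship and severity are to be summarised "for each treatment group irrespective of first or second dose for AE relationship and AE severity".

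SAP 5.4 contains a general rule: "Analyses based on the second dose will be done for both the rescue and recurrence subpopulations". SAP 5.1 records that the second-dose safety population was removed. It presents this as following from the choice of populations for the efficacy analyses.

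**The concern.** Second-dose safety belongs to the primary objective, and Protocol 10 says it will be looked at separately by the reason for redosing. The adverse event section of the SAP has no table that does so.

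This matters in practice because the rule for second doses changed during the study. Under Protocol 7.3.2 and 8.1 the only second dose still permitted is 100 mg after 100 mg, for recurrence. The amendment history shows that rescue use was permitted earlier. A single two-dose column for the 100 mg arm therefore mixes the remaining regimen with a use that has been withdrawn. The efficacy section does show the two reasons apart, so the benefit and harm of the remaining regimen could not be read side by side.

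The second part is simpler. The protocol promises relationship and severity by dose, and the SAP states the opposite without recording a change.

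**Working it through.** The plan has no figure to reproduce here: the sample size is not based on a hypothesis (Protocol 10.1) and the analyses are descriptive. The check compares planned outputs.

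1. **What the protocol asks for.** Protocol 10 names safety and two subsets, rescue and recurrence. Protocol 10.5.1 asks for adverse events, relationship and severity by arm and dose.

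2. **What SAP 12.1 delivers.** It has 16 table or listing items (15 in the main list plus the cardiovascular risk subgroup item) and 7 numbered points. Items naming rescue or recurrence: 0 of 16. Numbered points naming either: 0 of 7. Points 2 and 4 separate one dose from two. Point 5, the per-attack summary, disregards the second dose.

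3. **Contrast with efficacy.** Of the 8 subsections 11.2.1.1 to 11.2.1.8, 4 name the rescue and recurrence second-dose populations: 11.2.1.1 (pain-free), 11.2.1.2 (most bothersome symptom), 11.2.1.5 (symptoms) and 11.2.1.6 (pain relief).

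4. **Does SAP 5.4 fill the gap?** It states the rule without limiting it to efficacy, and SAP 5 opens by covering efficacy and safety endpoints. But SAP 12.1, which lists the adverse event outputs, does not apply it. SAP 5.6 says the final lock will provide the same tables as the May 2018 lock, so the list will not change unless someone edits it.

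5. **Is the departure recorded?** Protocol 10 requires changes of method, with their justification, to be described in the SAP and the study report. SAP 5.1 discloses removal of the second-dose safety population, with an efficacy reason. It does not mention the reason split for adverse events, or the change to relationship and severity.

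6. **Can events be assigned to one dose?** Often not. A TEAE is an event within 48 hours of a dose (SAP 12.1), and a second dose comes 2 to 24 hours after the first. The two windows overlap for 48 − 24 = 24 hours up to 48 − 2 = 46 hours. Relationship is also judged against study drug and not against a particular dose (Protocol 9.2.1). A split by number of doses in the attack is workable. A split that ascribes each event to the first or second tablet is not reliable.

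7. **Is the reason available?** SAP 4 defines rescue and recurrence. SAP 6 counts subjects redosing for each, with disposition also shown for the safety population. SAP 8.5 counts second-dose attacks by reason, with a missing category, in the ITT and mITT populations.

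**The case against.** The strongest reply is that the protocol does not clearly require this split for safety. Protocol 10.3.3 defines four second-dose populations, including a safety one, and then qualifies only the ITT, mITT and PP populations by reason. Protocol 10.7.1 and 10.7.2, which deal with each reason, describe efficacy outputs only. The wording in 10.5.1 can be read as one second-dose category, which the one-dose and two-dose tables would broadly satisfy. SAP 5.4 could be said to cover safety already. SAP 5.1 partly discloses the change. All safety values will also be listed (SAP 12).

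Much of this stands. It makes the protocol ambiguous and the departure smaller. It does not cancel Protocol 10, which names safety and two subsets, and a general rule that no table applies still leaves the output unspecified. The reply also does not meet the relationship and severity point: 10.5.1 asks for a split by dose and SAP 12.1 rules one out.

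A reader might infer three stronger claims that the documents do not support:

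- **That the primary objective is unmet.** It asks for second-dose safety and does not name the reason; points 2 and 4 report two-dose events by arm.
- **That the pooled column is biased by some number of percentage points.** The documents give neither the share of second doses taken for each reason nor event rates by reason, so any such figure would be assumed.
- **That the older second-dose wording left in Protocol 4 and 4.5 and SAP 2.1 and 5 permits redosing at 200 mg.** The protocol's dosing sections agree on the 200 mg cap in 24 hours, and doses taken under the earlier rule still need analysis. Tidying that text is an editorial matter, separate from this point.

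**Conclusion.** The point holds as a minor one. Protocol 10 plans second-dose safety by reason, and 0 of 16 items and 0 of 7 numbered points in SAP 12.1 deliver it. Relationship and severity lose the dose split planned in 10.5.1, with no safety reason in SAP 5.1. As listed, adverse events for 100 mg plus 100 mg for recurrence would be tabulated only together with rescue redosing.

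This rests on taking Protocol 10 at its word despite the narrower text in 10.3.3, and on reading SAP 12.1 as the full list of adverse event outputs. If the sponsor already intends SAP 5.4 to govern those tables, the gap is a missing line in 12.1. The population table in SAP 4 is partly lost in the extracted text, and nothing here rests on what it seems to omit. No numerical effect on the results is claimed.

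**What to change.** Apply SAP 5.4 explicitly to SAP 12.1, points 2 and 4:

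- Show the two-dose TEAE and SAE tables by arm and by reason: rescue, recurrence, missing.
- Assign the reason per attack, using the SAP 4 definitions. A subject with attacks of both kinds counts once in each column, so the columns need not add up to the arm total.
- Put second doses known only from the CRF, or without a usable time, under missing.
- Print counts beside percentages.

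For relationship and severity, show attacks treated with one dose apart from those treated with two. This respects Protocol 10.5.1 as far as the data allow without ascribing an event to one tablet. Otherwise, record the departure in SAP 5.1 with a reason that concerns safety.

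The cost is some extra columns and a few lines of text, with no new data and no change in conduct. Two drawbacks should be accepted openly. First, the missing column may be larger than the SAP 8.5 counts suggest, because safety analyses use CRF-confirmed doses, which can lack times. Second, the cells become smaller. With zero events the one-sided 95% upper limit is 1 − 0.05^(1/n): 5.8% for 50 subjects and 1.5% for 200 (illustrative sizes, not from the documents). Empty cells must therefore not be read as evidence of no risk.

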#### **12.1.1 Relationship to Study Drug**

Summaries of AEs by relationship to study drug will classify AEs as either:

- Reasonably or Possibly Related
- Not Reasonably or Possibly Related

Related AEs are those that are recorded on the AE CRF page as “Reasonably or Possibly Related” or those with a missing relationship.

#### **12.1.2 Adverse Event Severity**

Severity of AEs will be classified as one of the following:

- Mild
- Moderate
- Severe
- Life-threatening

If multiple severities are reported for a given adverse event for a subject, the highest severity reported will be used. Any adverse event with missing severity in the locked data base will not be summarized by severity.

#### **12.1.3 Adverse Events Leading to Discontinuation**

Adverse events leading to discontinuation of the study are those for which the answer to the AE CRF page's question of "Did the AE cause the subject to discontinue from the study?" is answered as "Yes."

#### **12.1.4 Serious Adverse Events**

Serious adverse events (SAEs) are those for which one or more of the following are indicated on the AE CRF page:

- Death
- Life-threatening
- Required or prolonged inpatient hospitalization
- Persistent or significant disability/incapacity
- Congenital anomaly
- Other medically important event

Subjects with "any serious adverse event" marked as "Yes" on CRF will be considered as serious AE even if one or more of the above specific events are not marked "Yes".

## **12.2 Clinical Laboratory Evaluation**

Laboratory results will be classified based on the reference ranges provided by the central laboratory.

For quantitative laboratory parameters, observed and change from baseline measurements will be presented by time point using descriptive statistics. Categorical urinalysis parameters will only be presented in a listing. Laboratory parameters will be presented in standards international (SI) units.

Shift tables describing out-of-reference range shifts will be provided for clinical laboratory test results, as appropriate by treatment group and dose based on the laboratory parameters as described below.

For each parameter, the out-of-reference range shifts will be classified as:

- Low
- Normal
- High

Shifts will be presented for lowest post baseline results and for highest post baseline results for all described laboratory parameters.

Laboratory blood data and urine data will be collected during **Screening/Visit 1 (ONLY** if more

than two weeks since **EoS/Visit 2** of COL MIG-301 or COL MIG-302) and at visit **Month 1/Visit 2, Month 6/Visit 4, and Month 12/Visit 6/EoS/ET**. If **Screening/Visit 1** is the same day the data will be used for both parent and Gladiator studies. In that case the baseline for this data will be considered from parent study (301 or 302) where subject was randomized previously, and respective lab parameters will be mapped by subject for new study for analysis. If **Screening/Visit 1** is within 2 weeks of **EoS/Visit 2** of COL MIG-301 or COL MIG-302 the data obtained will be used for both studies except a urine pregnancy test for WOCBP will be performed separately. In that case data for urine analysis will be used from current study. The question “When did the subject enter 305?” from CRF will be used to determine when the screening/Visit 1 for each subject was performed.

In the case of repeated laboratory values at the same visit, the last value collected will be used for the analysis.

Additionally, plots of ALT and AST vs. Total bilirubin by treatment group will also be produced, with reference lines at 3xULN for ALT, AST, and 2XULN for Total bilirubin. In each plot, Total bilirubin will be in the vertical axis.

The following laboratory parameters will be summarized:

- Hematology
  - White blood cell (WBC) count with differential (neutrophils, lymphocytes, eosinophils, monocytes, basophils),
  - hemoglobin,
  - hematocrit,
  - platelet count,
  - red blood cell (RBC) count
- Chemistry
  - Albumin,
  - alkaline phosphatase (AP),
  - alanine aminotransferase (ALT),
  - aspartate aminotransferase (AST),
  - blood urea nitrogen (BUN),
  - calcium,
  - chloride,
  - bicarbonate,
  - creatinine,
  - glucose,
  - phosphate,
  - potassium,

- sodium,
- total bilirubin,
- total protein,
- total cholesterol,
- zHDL,
- triglycerides.
- Urinalysis
  - Protein,
  - glucose,
  - nitrite,
  - ketones,
  - blood (hemoglobin),
  - pH,
  - specific gravity,
  - RBCs,
  - WBCs.

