Sample Size Rationale

The sample size was chosen to provide an appropriate long-term safety database. It is not based on statistical hypothesis.

Schedule of Assessments

Assessment	Visit 1 Screening and Baseline	Visit 2, 3, 4 and 5 (Months 1, 3, 6 and 9)	Visit 6/EoS/ ET¹
Obtain informed consent/HIPAA	X		
Review inclusion / exclusion criteria	X		
Review migraine history, medical history and concomitant medications	X		
MIDAS questionnaire	X	X	X
Review resource utilization (visits to specialists, ERs, etc.)	X	X	X
Complete physical examination	X		
Vital signs (heart rate, blood pressure)	X ²	X	X
Brief physical examination based on AE(s)	X ²	X	X
Weight	X		X
12-lead ECG	X ³	VISIT 4 ONLY	X
Clinical laboratory ⁴	X ³	VISIT 2 and 4	X
Urine pregnancy for women of child-bearing potential	X ^{5,6}	X ⁶	X ⁶
Columbia Suicide Severity Rating Scale	X ³	X	X
Randomization	X		
Dispense study drug, study diary, and provide detailed instructions	X	X	
Collect empty dosing card(s) and unused study drug. Review dosing compliance and diary		X	X
Migraine attack (electronic diary) documentation by subject		X	
Documentation of rescue/recurrence medication		X	X
Documentation of adverse events and concomitant		X	X

1. **ET** is for subjects that discontinue the study between scheduled visits. The patient should return to the clinic within 14 days of the decision to withdraw from the study. **EoS** is the designation for any scheduled visit that the subject discontinues at or Visit 6 (month 12).
2. Brief physical examination based on AE (s) and vital signs will be the values obtained from **EoS/Visit 2** of COL MIG-301 or COL MIG-302 only if subject signs consent and enrolls in COL MIG-305 on the same day.
3. Laboratory tests, ECG and C-SSRS will be the values obtained from **EoS/Visit 2** of COL MIG-301 or COL MIG-302, as long as the subject signs consent and enrolls in COL MIG-305 on the same day or within two weeks (14 days) of **EoS/Visit 2**.
4. Clinical laboratory tests include hematology, biochemistry, lipid profile and urinalysis. In the event of clinically significant laboratory findings, including but not limited to hepatic laboratory abnormalities, repeat or additional laboratory testing may be required outside of a scheduled clinic visit.
5. A urine pregnancy test for women of childbearing potential is required unless Visit 1 is same day as EoS/Visit 2 of COL MIG-301 or COL MIG-302.

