9.1.5.3 Hepatic Safety Monitoring

If a study subject experiences elevated ALT $\geq 3X$ ULN, AST $\geq 3X$ ULN, ALP $\geq 2X$ ULN, or elevated TBL $\geq 2X$ ULN, liver testing (Appendix 5) should be repeated within 3 to 5 days including ALT, AST, ALP, TBL, direct bilirubin, gamma-glutamyl transferase, and creatine kinase to confirm the abnormality and to determine if it is increasing or decreasing. If the abnormality persists or worsens, clinical and laboratory monitoring should be initiated by the investigator and in consultation with the study medical monitor. Monitoring of ALT, AST, TBL, and ALP should continue until levels normalize or return to approximate baseline levels.

Hepatic Safety Data Collection

Additional safety data should be collected if 1 or more of the following conditions occur:

- Elevation of serum ALT to $\geq 5X$ ULN on 2 or more consecutive blood tests
- Elevation of serum AST to $\geq 5X$ ULN on 2 or more consecutive blood tests
- Elevated serum TBL to $\geq 2X$ ULN (except for cases of known Gilbert's syndrome)
- Elevation of serum ALP to $\geq 2X$ ULN on 2 or more consecutive blood tests
- Subject discontinued from treatment due to a hepatic event or abnormality of liver tests
- Hepatic event considered to be a SAE

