## 5 GENERAL SPECIFICATIONS

This section details the specifications for summarizing all efficacy and safety endpoints.

All safety analyses will be based on the safety population. Efficacy analyses will be performed on ITT population, with the exception of the MBS-free and headache pain-free analyses secondary endpoint which will be performed on the mITT population.

Continuous variables will be summarized using descriptive statistics, i.e. n (number of subjects with available data), mean, median, standard deviation (SD), minimum, and maximum. For those measures that are analyzed using change from baseline scores, descriptive statistics will also be presented on observed scores, unless otherwise noted.

Minimum and maximum values will be presented to the same precision as the raw data. Mean and median will be presented to one more decimal place than the raw data. Standard deviation will be presented to two more decimal places than the raw data.

Categorical variables will be summarized using counts and percentages. Unless otherwise specified, percentages will be calculated using the numbers of subjects in the summarized population in each treatment group as denominators. Percentages will be presented with a precision of 1 digit after the decimal.

In this study, subject will enter the efficacy data on dosing and post-dose assessments in an e-diary. The e-diary records the date and time of the first dose and of the second dose and is programmed to assess specific time points and assessments as defined in the protocol based on the timing of the dose as recorded. This data is collected in the e-diary when e-diary is in migraine mode. Subjects will record the dosing information for every migraine attack in this study. Specifics of Migraine Mode are as below:

- Migraine Mode – First Dose
  - The e-diary enters Migraine Mode **ONLY** if the subject indicates taking his/her first dose of study medication
  - Post Dose Assessments will be completed using the Migraine Questions button at specific time intervals for up to 48 hours after the subject confirms taking study medication

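### SAP 12.2 plans no by-arm count and percentage of subjects reaching the liver cut-offs in Protocol 9.1.5.3, although cases can still be found in the listings

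*SAP*

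**What the plan says.** **Protocol 9.1.5.3** works in two tiers. A single ALT or AST of at least 3x ULN, or ALP or total bilirubin (TBL) of at least 2x ULN, prompts repeat liver tests within 3 to 5 days. The second tier reads "Additional safety data should be collected if 1 or more of the following conditions occur". Its analyte conditions are ALT or AST of at least 5x ULN on two or more consecutive tests, ALP of at least 2x ULN on two or more consecutive tests, and TBL of at least 2x ULN except in known Gilbert's syndrome. Two further conditions concern hepatic discontinuations and hepatic SAEs. Footnote 4 to the protocol's Schedule of Assessments adds that "repeat or additional laboratory testing may be required outside of a scheduled clinic visit".

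**SAP 12.2** plans four things for liver tests:
- Descriptive statistics by time point. "Laboratory parameters will be presented in standards international (SI) units", and SAP 5 defines the summary as n, "mean, median, standard deviation (SD), minimum, and maximum".
- Shift tables: "For each parameter, the out-of-reference range shifts will be classified as" Low, Normal or High. "Shifts will be presented for lowest post baseline results and for highest post baseline results for all described laboratory parameters".
- By-arm plots of ALT and AST against bilirubin, "with reference lines at 3xULN for ALT, AST, and 2XULN for Total bilirubin".
- A rule for repeats: "In the case of repeated laboratory values at the same visit, the last value collected will be used for the analysis".

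**Elsewhere**, SAP 12 lists all safety values by treatment group and subject. Protocol 10.5.2 has the listings mark out-of-range and clinically significant values. SAP 12.3 and 12.4, with Appendices 16.3 and 16.4, give frequencies and percentages of subjects meeting numeric criteria for vital signs and ECG intervals.

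**The concern.** Safety is the primary objective. For liver tests the protocol itself fixes the levels that call for action, and the natural question for each dose is how many subjects reached them, out of how many. The planned summaries answer a different question: how many subjects were above normal, and how large the largest value was at each visit. The SAP already answers the right kind of question for blood pressure, pulse, weight and ECG intervals. Without the liver equivalent, a reader comparing 100 mg with 200 mg must build the count by hand from listings or judge it by eye from a plot.

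**Working it through.** The documents state no figure on this point, so the check sets the texts side by side.

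**1. Each protocol cut-off against SAP 12.2**

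| Cut-off (x ULN) | Role in Protocol 9.1.5.3 | Where the SAP uses it | By-arm n (%) |
|---|---|---|---|
| ALT 3x | retest | plot line | none |
| AST 3x | retest | plot line | none |
| TBL 2x | retest; extra data unless Gilbert's | plot line | none |
| ALP 2x | retest; extra data if on consecutive tests | nowhere | none |
| ALT 5x | extra data if on consecutive tests | nowhere | none |
| AST 5x | extra data if on consecutive tests | nowhere | none |

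Six cut-offs: 3 are plot lines, 3 are named in no output, 0 have a count. ALP is not plotted at all.

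**2. The SAP's practice for other safety data**

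- Appendix 16.3: systolic 4 + diastolic 4 + either pressure 1 + pulse 3 + weight 2 = 14 criteria.
- Appendix 16.4: PR 2 + QRS 2 + QT 1 + QTcF 6 (low, sex-specific high, above 500, increases above 30, 60 and 75) = 11 criteria.

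**3. What the planned outputs can show**

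- *Shift tables:* High is any value above the reference range, whether 1.1x or 6x ULN.
- *Maxima:* given per visit (Months 1, 6 and 12) and in SI units. A maximum above 5x ULN at all three visits is compatible with one subject or many.
- *Listings:* every value is there by arm and subject, marked as out of range or clinically significant but not by multiple of ULN.
- *Plots:* points beyond 3x are visible, but there is no denominator, no 5x line and no ALP. The SAP does not say whether points are subject maxima or visit values.
- *AE tables:* these depend on the abnormality being recorded as an AE. Protocol Appendix 1 puts transaminases of 5.1 to 20.0 x normal in Grade 3, close to the 5x cut-off. Grade 2 runs from 2.6 to 5.0, so no grade boundary falls at 3x.

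**4. Illustration with assumed counts**

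The documents give no event rates. Assume 1,000 treated subjects per arm (2580 / 2 = 1,290 are planned per arm), the same number of High results and a largest ALT of 6x ULN in both arms. Subjects at 5x or more could still differ:

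| Subjects at 5x or more | Share of 1,000 | Exact 95% CI |
|---|---|---|
| 1 | 0.1% | 0.00 to 0.56% |
| 3 | 0.3% | 0.06 to 0.87% |
| 5 | 0.5% | 0.16 to 1.16% |
| 10 | 1.0% | 0.48 to 1.83% |

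One subject in one arm against 5 in the other (range 3 to 10) would give identical maxima and shift counts. A count table would show 0.1% against 0.5% (range 0.3% to 1.0%). The intervals show the precision of one cell and are not a comparison of arms.

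A zero count would also be informative. The one-sided 95% upper bound is 1 - 0.05^(1/n): 0.23% for n = 1,290, and 0.46% if only half (645, an assumption) were evaluable.

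**5. Last value or highest value**

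SAP 12.2 takes the last of repeated values at a visit, yet bases shifts on the highest post-baseline result, and does not say which rule is applied first. A 3-to-5-day repeat stored under the same visit could replace the abnormal value that prompted it in the visit summaries, and possibly in the shifts and plots. If the repeat is stored as unscheduled, the SAP does not say whether it enters the maximum. The documents do not show how repeats are labelled.

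**The case against.** The strongest reply is that no commitment is unmet. Protocol 10.5.2 asks for listings, observed and change values, and shift tables. SAP 12.2 delivers these and adds plots. Protocol 9.1.5.3 governs retesting and data collection, and requests no table. This stands. A reader might infer that the SAP contradicts the protocol, but the documents do not support that.

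A reader might also infer that liver cases would go unreported. They would not. The listings contain every value by arm. ALT and AST cases at 5x or more would normally lie beyond the 3x plot line, so 1 against 5 might well be seen there. An ALT of 6x ULN recorded as an AE would be Grade 3 and enter the severity summaries. The protocol's AE definition is open-ended, so a medical intervention is not a precondition. What is missing is a count with a denominator, and for ALP any display of the cut-off.

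A third tempting inference is that the last-value rule will erase peaks. That depends on visit labelling that the documents do not show. A natural reading is that the rule serves by-visit summaries while shifts use the true maximum. The text leaves this open, so one clarifying sentence is justified, but no loss is established.

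Finally, a table of single maxima would not match the protocol's extra-data criteria, which need consecutive tests for ALT, AST and ALP and exempt known Gilbert's syndrome. Limiting it to subjects below the cut-off at baseline would drop some who met a trigger. Both objections are right, and the fix allows for them.

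**Conclusion.** The point holds as a reporting weakness that should be corrected. By-arm counts and percentages are planned for 14 vital-sign and 11 ECG criteria but for 0 of the 6 liver cut-offs in Protocol 9.1.5.3. Three of those six appear only as plot lines and three in no output. No planned estimate, test or primary-endpoint result changes. What is lost is a direct statement, for each dose, of how many subjects reached the protocol's own action levels.

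The textual finding needs no assumption. The numerical illustration rests on assumed counts and 1,000 subjects per arm, and predicts nothing about this trial. One possible explanation is that the hepatic section came in with protocol amendment D, while the SAP's study summary still describes second doses for rescue and in both arms, which that amendment removed. The documents do not confirm this.

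**What to change.** Add to SAP 12.2 one descriptive table by arm for the Safety population, with n (%) of subjects in two blocks:

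- **Maximum post-baseline value (7 rows):** ALT at least 3x, ALT at least 5x, AST at least 3x, AST at least 5x, ALP at least 2x, TBL at least 2x, and ALT or AST at least 3x together with TBL at least 2x ULN.
- **Protocol extra-data criteria (4 rows):** ALT at least 5x, AST at least 5x and ALP at least 2x ULN, each on two or more consecutive tests, and TBL at least 2x ULN excluding known Gilbert's syndrome.

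Show the table for all subjects and for those below the relevant cut-off at baseline.

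State that the last-value rule applies only to by-visit summaries. The maximum used in this table, in the highest post-baseline shifts and in the liver plots should take all scheduled, repeat and unscheduled values. Because SAP 5.6 has the final lock repeat the interim-lock outputs, name the new table there too.

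The cost is one table of 11 rows in two versions and a short rule, from laboratory data already collected, plus identification of known Gilbert's syndrome from medical history. No new procedures are needed. The drawback is small counts per row, so the table should be descriptive, with no between-arm test.
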